## 6.2 Classification of Events

#### 6.2.1 Relatedness

The site Investigator will assess the relationship of SAEs to FMT, as related or not related, based on clinical judgment and using all available information, and may include consideration of the following factors:

- Possible alternative causes of the SAE, including the disease under treatment, pre-existing
  conditions, concomitant use of other drugs, and presence of environmental or genetic
  factors.
- The temporal association between FMT exposure and onset of the SAE.
- Whether the manifestations of the SAE are consistent with known actions or theoretical toxicity of FMT.

The causal relationship between FMT and the SAE will be assessed using one of the following categories.

- 1. Not Related:
  - Temporal relationship is lacking (e.g., the event occurred before FMT); or
  - Other causative factors explain the event (e.g. pre-existing condition, other concomitant treatment);
- 2. Possibly Related:
  - Positive temporal relationship (e.g., the event occurred within a reasonable time frame following FMT); and
  - The SAE is possibly explained by FMT and/or, and there is a lack of other causal factors.
- 3. Related:
  - Positive temporal relationship (e.g., the event occurred within a reasonable time frame following FMT); and
  - The SAE is more likely explained by FMT than by other causes.

## 6.2.2 Expectedness

Related or possibly related SAEs will be assessed as to whether they were expected or unexpected based on current knowledge regarding the effects of FMT. Events known to be associated with FMT, CDI, or IBD include the following:

- Diarrhea
- Constipation
- o Abdominal pain
- o Fever
- Sedation complication
- Bleeding
- Perforation
- o Bacterial infection
- Viral infection
- o Fungal infection
- o Parasitic infection

Events that are determined to be expected will be reported through the annual event summary report to the Sponsor and OSMB.

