## 2.2 Rationale for Study Objectives Measures

## 2.2.1 To assess short-term and long-term safety

The safety of FMT is currently the greatest concern related to its use, and characterizing the safety of FMT and subsequent gut-related-microbiota products is the primary goal of the Registry. Short-term adverse events (AEs) relate primarily to the method of delivery (e.g., colonoscopy) and to acute infections or other adverse events from the donor fecal material and should be readily definable and quantifiable. Of greater concern and uncertainty is the possibility of long-term AEs. The human-to-human transfer of feces may be associated with long-term health risks to the recipient because the gut microbiota is composed of many components that have not been characterized and can change over time in ways that cannot be currently predicted. It is imperative to determine if FMT leads to unintended development of serious conditions due to the transfer of gut microbiota. In addition to infections, the possibility that gut microbiota associated with a disease phenotype (e.g., obesity, diabetes, cardiovascular disease) will be transplanted and result in chronic disease in recipients must be assessed. A prospective registry in a large sample of patients with long-term follow-up is the only practical method to achieve this aim at present.

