## 6.4 Reporting Procedures

All spontaneous and pre-specified AEs reported by participants or healthcare providers will be recorded in the Registry database. Predefined short-term and long-term AEs are presented in *Supplements 5* and 6. Analyses of all AEs (including spontaneous and pre-defined AEs and SAEs) will be provided to the Registry Steering Committee and the OSMB at least twice yearly for their review. Summaries of AEs (including spontaneous and pre-defined AEs and SAEs) will be submitted to IRB and NIH during the annual review of the registry.

Breach of privacy and suspected unexpected SAEs will be reported to the Registry Steering Committee Chair and Co-Chair and the OSMB within 5 days of identification of the event. These events will also be reported to the local site IRB per local reporting criteria.

All participants are given a toll-free number to contact the Investigators directly if they have any safety issues or concerns.

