## 8.2 Interim Monitoring and Early Stopping

The Registry will have no formal interim analysis or early stopping plan. Regular monitoring of the safety and effectiveness data will be performed by the Registry Steering Committee and OSMB. Regular review of analyses of safety and effectiveness will occur twice yearly. In addition, breaches of privacy or suspected unexpected SAEs will be reported to the Registry Steering Committee Chair and Co-Chair and the OSMB within 5 business days after the event is identified.

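### The expectedness list in section 6.2.2 names four unqualified infection classes, so a serious infection suspected to come from donor stool or product can lose the 5-day report

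*Protocol*

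**What the plan says.** Protocol section 6.2.1 has the site Investigator grade each SAE as not related, possibly related or related to FMT. One ground for not related is "Other causative factors explain the event (e.g. pre-existing condition, other concomitant treatment".

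Section 6.2.2 takes the related and possibly related SAEs and asks whether each was expected, "based on current knowledge regarding the effects of FMT". The reference list follows at once, introduced by "Events known to be associated with FMT, CDI, or IBD include the following". Four of its eleven entries are bacterial, viral, fungal and parasitic infection, each without a qualifier. The section closes with the route for expected events: "Events that are determined to be expected will be reported through the annual event summary report to the Sponsor and OSMB".

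Section 6.4 sets the fast route: "Breach of privacy and suspected unexpected SAEs will be reported to the Registry Steering Committee Chair and Co-Chair and the OSMB within 5 days". Section 8.2 repeats it for the same two kinds of event, but with the clock "within 5 business days after the event is identified". Section 6.4 also says that analyses of all AEs, expected or not, "will be provided to the Registry Steering Committee and the OSMB at least twice yearly".

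Safety is the primary objective. Section 2.2.1 names "acute infections or other adverse events from the donor fecal material" among the main short-term risks, and section 1.2 recalls the transmission of hepatitis C and HIV through human-derived material as a reason for caution.

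**The concern.** The 5-day report is the only case-level alert to the OSMB in the protocol, and it depends on the word unexpected. A related SAE of, say, viral hepatitis or drug-resistant bacteraemia matches a listed infection class. An assessor who takes the list at face value will call it expected, and the alert is lost. No section makes an exception where the donor or product is the suspected source.

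This matters because one such case can be informative. Section 1.1 foresees stool banks as suppliers and Supplement 1 records batch and lot numbers, so one source may serve more than one recipient. Section 6.2.2 also gives no rule on source and does not say who judges expectedness, so similar cases may be handled differently across the 75 planned sites.

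**Working it through.** The protocol gives no figure on this point to reproduce. The check follows one event through the reporting rules and then compares waiting times.

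**Path of a serious infection with the donor stool or product as suspected source**

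1. Section 6.2.1: timing fits and no other cause explains it, so it is graded related or possibly related and goes on to expectedness.
2. Section 6.2.2: the test is current knowledge of FMT effects. The list printed under the test covers events linked to FMT, CDI or IBD and contains the matching infection class. Either answer is open.
3. If unexpected: Steering Committee Chair, Co-Chair and OSMB within 5 days (6.4) or 5 business days (8.2).
4. If expected: no fast report. The OSMB sees it in the analyses of all AEs at least twice yearly (6.4) and in the annual summary (6.2.2).

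The slower path covers HIV and viral hepatitis, which Supplement 6 lists as serious infections and which fit the class of viral infection. Prion disease, listed beside them, does not clearly fit any of the four classes and may still count as unexpected.

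**Wait from identification to the OSMB**

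Assumptions: exactly two reviews a year, evenly spaced (the stated minimum), and identification equally likely at any time between reviews.

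- Longest wait = 365.25 / 2 = 182.6, about 183 days.
- Average wait = 182.6 / 2 = 91.3, about 91 days.
- Fast route: 5 days at most; 5 business days normally span 7 calendar days.

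**Counted from FMT, for an infection first identified on an on-time 1-month form (day 30)**

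- Fast route: 30 + 5 = day 35 at the latest (30 + 7 = day 37 on business days).
- Periodic route: 30 + 91.3 = about day 121 on average; 30 + 182.6 = about day 213 at most.

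These are days after FMT, not days after onset of infection. A spontaneous report could bring identification before day 30. Under section 6.1 sites give AE data at 1, 6, 12 and 24 months, so a later infection may wait longer to be identified. That lag is the same on both routes, and the difference between the routes is unchanged.

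**Extra fast reports if such infections always took the 5-day route**

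The documents give no rate. For illustration only, at an assumed 1 to 5 qualifying SAEs per 1,000 patients: 4,000 x 0.001 = 4 and 4,000 x 0.005 = 20 over the whole registry, or 4 / 75 = 0.05 to 20 / 75 = 0.27 per site.

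**The case against.** The strongest reply is that section 6.2.2 never says the listed events are expected. The list describes associations, the test is current knowledge, and an assessor who suspects transmission can already call the event unexpected. That stands: a reader might infer that the protocol declares all infections expected, and the text does not support it. The answer is only that a list placed directly under the test, with no other criterion, makes expected a natural label.

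Three further inferences also go too far.

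- **That the OSMB waits a year.** The annual summary is not its only source; section 6.4 gives it all AEs at least twice yearly, and more frequent reviews would shorten the wait.
- **That the infections left after the relatedness step are mainly donor transmissions.** Infection after a perforation or a sedation complication could also be graded related to FMT, and the documents do not show the mix.
- **That the gap causes avoidable cases.** This is a registry of ordinary care. Under section 7.2 the OSMB comments and recommends, and it has no stated power to stop FMT or hold back a lot.

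Other safeguards are real: AEs go to the site IRB under section 6, and Supplement 5 records organism and relatedness. Neither is a case-level alert to the OSMB.

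Finally, a rule resting on suspected source alone would swap one undefined judgement for another. That is fair, and the fix below therefore names the assessor and gives a criterion.

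**Conclusion.** The point holds as a cheap improvement to safety reporting. As written, sections 6.2.2, 6.4 and 8.2 allow a related or possibly related serious infection with the donor stool or product as suspected source to be classed as expected and so to lose the 5-day report to the Steering Committee Chair, Co-Chair and OSMB. They do not require it.

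Where it happens, the OSMB learns of the case up to about 183 days after identification, about 91 on average, instead of within 5. These figures rest on two evenly spaced reviews a year. The benefit of a change is an earlier alert. No estimate or analysis is affected, and how many patients are concerned, or share a donor or lot, cannot be derived from the documents.

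**What to change.** Add to sections 6.2.2, 6.4 and 8.2:

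*Any related or possibly related infection SAE for which the site Investigator cannot exclude the donor stool or product as source (that is, not C. difficile recurrence and not a documented complication of the delivery procedure) is reported by the 5-day route, whatever its expectedness.*

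Leave the expectedness list, the annual summary and the twice-yearly analyses as they are. Use one clock, 5 days or 5 business days, in both 6.4 and 8.2.

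The cost is one sentence in three places and a small number of extra expedited reports, at a rate the documents do not give. The fast route, the OSMB, the organism and relatedness fields in Supplement 5, and site training on reporting unexpected events (section 3.2) are already in place. The new element is the Investigator's judgement of source, which that training should cover.

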## 6.3 Serious Adverse Events (SAE)

The only type of adverse event that may occur related to participation in the FMT registry is breach of privacy/confidentiality.

Clinical SAEs that are recorded in the registry will have the standard definition, which includes the following:

- Death
- Life-threatening (patient was at substantial risk of dying)
- Hospitalization (initial or prolonged)
- Disability or permanent damage
- Congenital anomaly/birth defect
- Other important event (may jeopardize patient and may require to prevent one of other outcomes)

## 6.4 Reporting Procedures

All spontaneous and pre-specified AEs reported by participants or healthcare providers will be recorded in the Registry database. Predefined short-term and long-term AEs are presented in *Supplements 5* and 6. Analyses of all AEs (including spontaneous and pre-defined AEs and SAEs) will be provided to the Registry Steering Committee and the OSMB at least twice yearly for their review. Summaries of AEs (including spontaneous and pre-defined AEs and SAEs) will be submitted to IRB and NIH during the annual review of the registry.

Breach of privacy and suspected unexpected SAEs will be reported to the Registry Steering Committee Chair and Co-Chair and the OSMB within 5 days of identification of the event. These events will also be reported to the local site IRB per local reporting criteria.

All participants are given a toll-free number to contact the Investigators directly if they have any safety issues or concerns.

## 7 Registry Oversight

## 7.1 Steering Committee

The FMT Registry Steering Committee will oversee the FMT Registry. This Steering Committee will report to the AGA Center for Microbiome Research and Education Scientific Advisory Board, which reports to the AGA Governing Board. The Steering Committee will be comprised of the individuals listed on the FMT Registry Protocol as Principal Investigators (PIs) and Co-Investigators. Two PIs, [name], will serve as the Chair and Co-Chair of the Steering Committee and will be responsible for the daily management of the registry and its associated activities (e.g., site selection, recruitment, IRB requirements, data management). The contact PI, [name], as Chair of the AGA Center for Microbiome Research and Education Scientific Advisory Board will serve on the steering committee in an *ex officio* capacity. The other members of the steering committee, comprised of the co-investigators, include representatives of key organizations that have helped to develop the registry and have an interest in its execution (IDSA, NASPGHAN, CCFA) as well as experts in clinical epidemiology and information technology.

## 7.2 Observational Study Monitoring Board

An independent OSMB will be established to monitor the registry performance and data in order to protect the safety and privacy of participants and to ensure the integrity and credibility of the registry. OSMB members will have no involvement in the FMT registry and no vested scientific or financial interest in the registry. OSMB members will include a data scientist with experience in epidemiology and registries, and at least two other members with expertise in clinical investigation, FMT, and/or the gut microbiome. It is anticipated that the OSMB will meet at least twice yearly and will review information on the registry conduct and results, including recruitment and retention, deviations from registry protocol, breaches of confidentiality, characteristics of participants, and safety and effectiveness outcomes. The OSMB will produce minutes for each meeting and provide any comments or recommendations regarding registry conduct or participant safety/privacy to the FMT Registry Steering Committee.

#### 7.3 Data Access and Publication Committee

A Data Access and Publication Committee will be established to review requests from investigators to access and perform analyses of registry data for purposes of scientific presentation and publication. This committee will ensure that the request is appropriate and within the scope of the

registry. It is anticipated that all appropriate requests for data will be granted. Once approved, data requests will be forwarded to ACI Clinical for processing. The investigators will be asked to adhere to the data sharing agreement, which includes credit to FMT Registry and the R24 as the source of the data on subsequent publications, abstracts, and other presentations.

## 7.4 Funding Sources and Conflicts of Interest

The FMT Registry is funded with a grant provided by the National Institute of Allergy and Infectious Diseases at the National Institutes of Health.

All investigators are required to conduct themselves at all times in accordance with Good Clinical Practices. Investigators are expected to commit themselves to ethical and professional conduct of clinical research. Commitment to preserving the physician's, medical community, and public's trust is ensured by conducting research at the highest scientific and ethical standards. Disclosure of any potential conflict of interest strengthens this trust. The COI review process will be:

- An AGA COI disclosure form and confidentiality statement is to be completed by all
  Investigators, including Steering Committee, OSMB members and Data Access and
  Publications Committee members, at the start of the project and updated at least
  annually thereafter, for 1 year post appointment/tenure.
- The content of the disclosure is the responsibility of each Investigator. The Investigator is expected to complete the statement, sign and submit it in writing to the AGA prior to engaging in research. It will then be forwarded to the AGA Institute Ethics Committee, who will report the existence of a conflict, if present, to the subcommittee, committee or task force chair as appropriate.
- The Ethics Committee is authorized to disqualify a candidate for Registry committees or the OSMB who fails to make a disclosure or who does not agree to resolve the conflict prior to assumption of their position.
- The disclosure statement is required to be completed even if no conflict exists.
- Disclosure and confidentiality statements will be held in a confidential file maintained by the national office. Access to the file will be available to appropriate AGA staff, the AGA Institute Ethics Committee, and the AGA Institute Governing Board only.
- Members adversely affected by this policy may request the Ethics Committee review
  the issue and recommend to the Governing Board that application of the policy be
  waived for compelling reasons.
- Reporting financial interest to the AGA Institute does not replace the need to comply with federal COI requirements.

## 8 Statistical Plan

## 8.1 Sample Size Determination and Power

As noted in the AHRQ's Registry User's Guide, registries are used to provide precise estimates of outcomes in real-world practice and document that potential adverse events occur at less than a pre-specified incidence with a predefined level of confidence. Plans for the FMT registry include a sample size of approximately 4,000 patients, which will provide precise estimates of incidence rates for common and rare events. For example, if the incidence of an outcome after FMT in the Registry population is 5.0%, the 95% CI will be 4.4% to 5.7%, indicating a precise estimate of treatment effect. The planned sample size will also provide high confidence in ruling out rare adverse events. If an adverse event does not occur in the planned population of 4000 patients, we will have 95% confidence that the adverse event occurs at a rate of less than one in a thousand patients undergoing FMT.

The FMT registry also will support comparative effectiveness studies focusing on different methods of delivery of FMT (e.g., colonoscopy, enema, upper GI endoscopy, nasogastric or nasointestinal tube). Statistical power for comparative effectiveness studies will depend upon the incidence of the outcome and the distribution of use of the different methods of delivering FMT. For example, assuming an outcome that occurs in one out of 1,000 FMT procedures using one delivery method, there would be 90% power to detect a difference between an incidence of 0.001 and 0.008 assuming that 2,000 patients were exposed to each of the two delivery methods. For more common outcomes, the statistical power for specific relative risk estimate is greater. For example, with 2,000 patients in each group there would be 90% power to detect a difference between two approaches for which the incidence rates of events were 3% and 5% (i.e., RR=1.67).

## 8.2 Interim Monitoring and Early Stopping

The Registry will have no formal interim analysis or early stopping plan. Regular monitoring of the safety and effectiveness data will be performed by the Registry Steering Committee and OSMB. Regular review of analyses of safety and effectiveness will occur twice yearly. In addition, breaches of privacy or suspected unexpected SAEs will be reported to the Registry Steering Committee Chair and Co-Chair and the OSMB within 5 business days after the event is identified.

## 8.3 Statistical Methods

The registry will be designed in a manner that will facilitate statistical analyses for the purpose of signal detection, generation of descriptive data, and the conduct of comparative effectiveness studies. There will be several major advantages of the registry design as opposed to a system of spontaneous reporting. Most importantly, a prospective cohort of patients who undergo FMT with collection of predefined outcomes will allow accurate estimation of incidence rates. In contrast, systems that rely on spontaneous reporting have incomplete numerator data and lack denominator data. The ability to calculate incidence rates greatly facilitates both descriptive epidemiology and signal detection.

As noted above, registries are used to provide precise estimates of outcomes in real-world practice and document that potential adverse events occur at less than a pre-specified incidence with a predefined level of confidence. Thus, descriptive statistics with 95% confidence intervals will be determined for the safety and effectiveness outcomes to provide precise estimates of incidences. As mentioned above, if an adverse event does not occur in the planned population of 4,000 patients, we will have 95% confidence that the adverse event occurs at a rate of less than one in a thousand patients undergoing FMT.

To increase our ability to study unanticipated adverse events, we will include a retrospective control group of patients with recurrent CDI identified from insurance claims using Optum Insight Life Sciences, Inc data. Using these data, we can determine the incidence of relevant outcomes in a group of patients with recurrent CDI treated with antibiotics rather than FMT. The incidence of relevant outcomes in this group can be compared to the patients treated with FMT in the registry. To assure the feasibility of this approach, we have conducted a preliminary analysis of these data to identify the number of patients who will be included in the control cohort. Recurrent CDI was defined as having a physician-made diagnosis of CDI (ICD-9 008.45) treated with 3 separate courses of antibiotics with metronidazole, vancomycin, or fidaxomicin (at least one of which were vancomycin or fidaxomicin). The 3 antibiotic prescriptions had to be at least 10 days apart and the third course needed to be started within the 90 days following the CDI diagnosis. We identified 4,313 patients meeting this definition with mean follow-up of 1.70 years. The sample size should be sufficient to address questions on relatively rare outcomes. For example, at age 68 years (the median age in our control cohort), the probability of death in the next 12 months is 1.75% and the expected survival is 18.8 years (CDC lifetables). With an average follow-up time of 1.70 years, assuming equal number of subjects undergoing FMT and equal follow-up time, we would have 90% power to detect a hazard ratio of 0.77 for a difference in survival rates between FMT and antibiotic treated patients.

As mentioned above, the FMT registry also will support comparative effectiveness studies focusing on different methods of delivery of FMT. Comparative effectiveness studies rely on the ability to adequately account for differences between the treatment groups. The FMT registry will facilitate this by collecting robust data on the indications for therapy and other covariates that describe the recipients and the methods of delivery. Such data will support standard statistical methods including logistic, Cox, and other regression methods, and the development of propensity scores and risk scores for risk adjustment.

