## 3 STUDY DESIGN

## 3.1 Overview Study Design Summery

This registry will prospectively enroll 4,000 patients who undergo FMT at 75 sites throughout North America. Information on FMT methodology employed (e.g., screening of donor and recipient, preparation, FMT delivery) will be collected from each site. The indication for FMT as well as baseline information on recipient will also be collected. Following FMT, patients will be followed at regular intervals up to 10 years post FMT. This will include follow-up information from the patient's healthcare provider at 1 month, 6 months, 1 year, and 2 years after FMT as well as direct communication with patients at least annually up to 10 years after FMT. Follow-up information collected will be designed to assess potential short-term and long-term safety and effectiveness.

Anticipating changes in therapy from current FMT to use of other gut-related microbiota products in coming years, the Registry will be constructed with the flexibility to collect methodological and follow-up clinical information for all forms of gut-related-microbiota products and for a variety of indications besides CDI and IBD.

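### The bound of less than one in a thousand and the 4.4% to 5.7% interval assume all 4,000 patients are observed; they suit 30-day outcomes, but are stated for all adverse events with no allowance for loss over 10 years.

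*Protocol*

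**What the plan says.** Section 8.1 opens its zero-event statement with "If an adverse event does not occur in the planned population of 4000 patients". Section 8.3 repeats it: "if an adverse event does not occur in the planned population of 4,000 patients, we will have 95% confidence" that the event "occurs at a rate of less than one in a thousand patients undergoing FMT". Section 8.1 also gives the precision of a 5.0% incidence as a 95% CI of 4.4% to 5.7%. Neither section names a time horizon, separates early from late events, or says whether the bound is one- or two-sided. Section 8.3 adds that "descriptive statistics with 95% confidence intervals will be determined for the safety and effectiveness outcomes".

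Section 2.1 makes short-term and long-term safety the primary objective, and Section 2.2.1 calls long-term events the greater concern. Under Section 3.1, "patients will be followed at regular intervals up to 10 years post FMT". Provider reports stop at 2 years. After that, information comes from "direct communication with patients at least annually up to 10 years after FMT", by email and text (Section 6.1). Section 4.4 lets participants leave at any time and bars further data collection once consent is withdrawn. No expected rate of loss, and no expected number under observation at any horizon, is given.

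**The concern.** A zero-event bound depends on how many patients were watched for long enough to have the event. At 30 days that number should be close to the number enrolled. At 5 or 10 years it will be smaller, by an amount the protocol does not estimate. A single figure based on 4,000 and applied to every adverse event therefore promises the same reassurance for late cancer or cardiovascular disease (Supplement 6) as for a procedural complication (Supplement 5).

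The two figures are part of the sample-size rationale for the primary objective. Quoted later for long-term harms, the bound could claim that a risk of 1 in 1,000 is excluded when the observed follow-up does not exclude it.

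**Working it through.** **Inputs.** N = 4,000, zero events, 95% confidence and a threshold of 0.001 (Sections 8.1 and 8.3); horizon 10 years (Section 3.1). Annual loss is not in the protocol, so the rates below are assumptions.

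**1. The plan's own figures.** The exact upper bound for zero events in n patients is 1 − α^(1/n).
- One-sided (α = 0.05): 1 − 0.05^(1/4000) = 0.00075.
- Two-sided 95% (α = 0.025): 1 − 0.025^(1/4000) = 0.00092.

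Both are below 0.001, so the statement reproduces. For 200 events in 4,000, the Wilson 95% interval is 4.37% to 5.72%, which matches the stated 4.4% to 5.7%.

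**2. Number needed.** Solve 1 − α^(1/n) = 0.001, so n = ln(α)/ln(0.999).
- One-sided: ln(0.05)/ln(0.999) = 2,994.2, so 2,995.
- Two-sided: ln(0.025)/ln(0.999) = 3,687.03, so 3,688.

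**3. Tolerated loss.** A patient who dies without the event is counted as fully observed, because that patient's outcome is known for a crude cumulative risk.
- One-sided: (4,000 − 2,995)/4,000 = 25.1% in total; 1 − (2,995/4,000)^(1/10) = 2.85% a year.
- Two-sided: (4,000 − 3,688)/4,000 = 7.8% in total; 1 − (3,688/4,000)^(1/10) = 0.81% a year.

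The annual figures apply the loss to all 4,000. Patients who have died can no longer be lost, so they are slightly strict. The total-loss figures do not depend on this.

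**4. Assumed annual loss over 10 years.** n = 4,000 × (1 − r)^10.

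| Loss a year | Observed to 10 years | One-sided bound | Two-sided bound |
|---|---|---|---|
| 2% | 3,268 | 1 in 1,091 (holds) | 1 in 886 (fails) |
| 5% | 2,395 | 1 in 800 (fails) | 1 in 650 (fails) |
| 10% | 1,395 | 1 in 466 (fails) | 1 in 379 (fails) |

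**5. The CI example.** For a 5% incidence the Wilson interval is 4.3% to 5.8% with 3,268 observed, 4.2% to 5.9% with 2,395 and 4.0% to 6.3% with 1,395. The change is small unless loss is heavy.

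**6. Person-time instead of completers.** If the event rate is constant, those who leave early still contribute. Person-years = 4,000 × (1 − (1 − r)^10)/(−ln(1 − r)), and the 10-year bound is about 10 × 2.996/person-years (one-sided, no deaths).
- 2%: 36,218 person-years, 0.83 per 1,000.
- 5%: 31,292 person-years, 0.96 per 1,000.
- 10%: 24,727 person-years, 1.21 per 1,000.

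The limit is then about 5.9% a year. For a harm that appears only late, early person-time does not help. At 5% loss the average number under observation in years 5 to 10 is 4,000 × (0.95^5 − 0.95^10)/(5 × 0.0513) = about 2,730, below 2,995.

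**The case against.** The strongest defence is that nothing in the sentence is miscalculated. It is conditional on no event in 4,000 patients, it names no horizon, and for 30-day outcomes it should hold even with loss up to 25.1% (one-sided). All of that stands. The fault is that an assumption of full observation is left unstated and unlimited, not that the arithmetic is wrong.

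Second, the protocol does work at retention: yearly gift cards (Section 4.5), automatic electronic contact (Section 9.1), a request for final information at departure (Section 4.4.2) and review of retention by the monitoring board (Section 7.2). These may keep loss under 2.85% a year, but no target or expected rate is stated against which to judge that.

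Third, person-time methods tolerate more loss, as step 6 shows. That stands for events with a constant rate and not for late-onset harms. Fourth, competing-risk estimation and censoring rules usually belong in a statistical analysis plan, which is not shown. Their absence is not the complaint. The complaint is the denominator that Sections 8.1 and 8.3 already fix.

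A reader might also infer that mortality alone uses up nearly all the margin, since Section 8.3 states that "the probability of death in the next 12 months is 1.75% and the expected survival is 18.8 years". The document does not support this. Those figures are for age 68, the median of the retrospective claims cohort, while the registry takes all ages, children included (Section 4.1). The course of mortality over 10 years would have to be assumed. Above all, the stated rate is per patient undergoing FMT, so an event-free death is a completed observation and not a loss. Even if death ends observation, on a Gompertz curve fitted to those two figures, constant-rate person-time still tolerates about 3.8% loss a year.

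Nor are the bound and the CI the only support for the sample size. Section 8.1 also covers comparisons of delivery methods, and Section 8.3 a survival comparison with the claims cohort.

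**Conclusion.** The concern holds in limited form. The bound and the CI are correct for 4,000 fully observed patients and appropriate at 30 days. As statements about safety to 10 years they are unqualified: the zero-event bound survives only if total loss stays at or below 25.1% one-sided, or 7.8% two-sided. The sidedness matters, because at 2% loss a year the bound holds one-sided and fails two-sided. The effect on the CI example is minor.

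The result rests on counting event-free deaths as observed and on requiring observation to the horizon, which is the relevant condition for late-onset harms. Whether the limit will actually be crossed cannot be said, because the protocol gives no loss rate. This is a modest point about the wording and scope of a stated assurance, and it does not show that 4,000 patients are too few.

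**What to change.** - In Sections 8.1 and 8.3, limit the 4,000-patient bound and the 4.4% to 5.7% interval to 30-day outcomes, and say whether the bound is one- or two-sided.
- For later horizons, state the zero-event bound from the number observed to that horizon (about 3 divided by that number, one-sided), or as a rate from the person-years observed (about 3 divided by person-years). Give the assumed annual loss and say how deaths are counted. If person-years are used, say that a constant event rate is assumed.
- Estimate long-term risks by cumulative incidence, with death as a competing event and censoring at last report, and show the number still under observation beside each estimate.

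The cost is a few sentences and a standard estimator. No change to enrolment or data collection is needed. The downside is that the stated long-term assurance becomes less favourable: for example 1 in 800 instead of less than 1 in 1,000 if 5% a year were lost.
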